4.8 OTHER ANALYSES

4.8.1 PK analyses

4.8.1.1 *Non-compartmental analysis: following the 1st administration*

Individual concentrations and PK parameters of drug at Cycle 1 will be listed and summarized by descriptive statistics (such as the number of observations, arithmetic and geometric mean, median, SD, standard error (SE), coefficient of variation (CV)%, minimum, and maximum) by cohort and possibly overall.

Mean concentration profiles over time will be plotted by cohort and possibly overall under the responsibility of Sanofi, Pharmacokinetic, Dynamic and Metabolism (PKDM), Translational Medicine and Early Development (TMED) department.

4.8.1.2 Over treatment concentrations: C_{trough} and C_{eo}

C_{trough} defined as a sample collected before dosing, in a time window of 6 to 8 days after the previous infusion for the QW administration, in a time window of 12 to 16 days after the previous infusion for the Q2W administration, will be included in the descriptive analysis irrespectively of interruption of infusion. However, C_{trough} drawn outside time collection window described in the protocol PK flowcharts or collected after a dose deviation higher than $\pm 50\%$ from intended dose will be excluded from the analyses.

C_{eo} collected after significant infusion interruption, drawn outside collection of time window described in the PK flowcharts of the protocol or collected after a dose deviation higher than $\pm 50\%$ from intended dose will be excluded from the analyses.

Individual C_{trough} and C_{eo} will be listed and summarized with descriptive statistics (such as the number of observations, arithmetic and geometric mean, median, SD, SE, CV%, minimum, and maximum) by cohort and possibly overall.

Mean ($\pm SE$) of C_{trough} will be plotted over treatment phase by cohort and possibly overall.

Individual C_{trough} ratio (C2D1 vs C1D8 and C3D1 vs C1D8) and C_{eo} ratio (C2D1 vs C1D1 and C3D1 vs C1D1) will be listed and summarized by descriptive statistics as described above by cohort and possibly overall.

All concentration values below the LLOQ will be treated as zero in individual listing and respective descriptive statistics and will be replaced by LLOQ value for individual ratio and respective descriptive statistics.

4.8.1.3 Population PK analysis

Details of the population PK analysis plan will be provided in a separate document.

4.8.2 Immunogenicity analyses

Immunogenicity impact on PK analysis may be explored, depending on the ADA prevalence.

Descriptive statistics of C_{trough} as described above will be provided at each cycle in the subset of negative participants by cohort and possibly overall where positive or inconclusive participants will be observed.

The impact of immunogenicity on PK will be assessed graphically by plotting individual C_{trough} profiles of ADA positive participants (and the concentration of the administered drug at the same time as ADA positive result will be notified) along with mean ($+/- SD$) C_{trough} profile of ADA negative participants by cohort and possibly overall. Descriptive statistics of C_{trough} of ADA negative participants will be provided by cycle at the bottom of the plot.

The impact on safety and efficacy endpoints may be further explored by graphical methods or descriptively, depending on the ADA prevalence.

4.8.2.1 Analysis of Immunogenicity variables

A summary table by cohort and possibly overall with the number (%) of pre-existing ADA and negative participants at baseline, number (%) of boosted and induced participants (either transient, persistent or indeterminate) will be reported, along with descriptive statistics of titer. Prevalence and incidence will also be presented.

In addition, for positive ADA participants, time to onset, duration of ADA response, and the characterization of the immune response (transient, persistent, indeterminate) will be provided using a summary table by cohort and possibly overall.

An individual data listing with ADA samples status (positive, negative or inconclusive), the titer if applicable, date of first/last dose, duration of exposure, study period (cycle), time point and date/time of sampling along with C_{trough} value of the drug will be provided for positive and inconclusive ADA participants.

Note that treatment-boosted ADA are excluded from the analyses of ADA kinetics because this type of immune response differs mechanistically.

4.8.3 Biomarker analyses

Blood samples before and after treatment with IMP (isatuximab) will be collected from all participants for the:

- flow cytometric analysis of immune cells: the percentage and the cell count of each immune cell population and sub-population will be summarized using descriptive statistics at each timepoint. Change from baseline will be also described to assess the biological effects of IMP on immune cell populations. A specific focus will be done on CD38 expressing cells in blood to evaluate its alteration upon IMP treatment. Baseline expression of immune cells, especially CD38 expression cells, may be also associated with the observed clinical responses in reduced anti-HLA antibodies to anti-CD38 treatment.
- possible functional assessment of memory B-cells depletion: peripheral B-cells will be processed for subsequent analysis of anti-HLA alloreactivity upon IMP treatment
- measurement of total immunoglobulin levels: descriptive statistics will be used to summarize the total immunoglobulin levels and the levels of ImmunoglobulinG (IgG) at each timepoint and the change over time in order to estimate the impact of IMP treatment on the total IgG pool. Baseline levels of immunoglobulin may be also associated with the observed clinical responses in reduced anti-HLA antibodies to anti-CD38 treatment.

4.9 INTERIM ANALYSES

Not applicable.

5 SUPPORTING DOCUMENTATION

5.1 APPENDIX 1 LIST OF ABBREVIATIONS

ADA:	anti-drug antibodies
ADI:	actual dose intensity
AEs:	adverse events
AESIs:	adverse events of special interest
AMR:	antibody mediated rejection
CKD:	chronic kidney disease
cPRA:	calculated panel reactive antibodies
CV:	coefficient of variation
DL:	dose level
DoR:	duration of response
E/D:	early discontinuation
ECG:	electrocardiogram
eHR:	electronic health record
FUP:	follow-up period
HLA:	human leukocyte antigen
HLGT:	high level group term
HLT:	high level term
ICF:	informed consent form
IgG:	ImmunoglobulinG
IMP:	investigational medicinal product
IRs:	infusion reactions
LCD:	likelihood of compatible donor
LLN:	lower limit of normal
LLOQ:	lower limit of quantification
LLT:	lower level term
MedDRA:	Medical Dictionary for Regulatory Activities
MFI:	mean fluorescence intensity
NCI-CTCAE:	National cancer institute common terminology for adverse events
OPO:	Organ Procurement Organizations
OPTN:	Organ Procurement and Transplant Network
PCSA:	potentially clinically significant abnormality
PDI:	planned dose intensity
PK:	pharmacokinetics
PKDM:	Pharmacokinetic, Dynamic and Metabolism
PT:	preferred term
RDI:	relative dose intensity
RR:	response rate
SAB:	single antigen bead
SAEs:	serious adverse events
SAP:	statistical analysis plan

SD:	standard deviation
SE:	standard error
SoA:	schedule of activities
SOC:	system organ class
TE:	treatment-emergent
TEAE:	treatment-emergent adverse event
TMED:	Translational Medicine and Early Development
ULN:	upper limit of normal
ULOQ:	upper limit of quantification
UNOS:	United Network for Organ Sharing
US:	United States
WHO-DD:	World Health Organization-drug dictionary

5.2 APPENDIX 2 CHANGES TO PROTOCOL-PLANNED ANALYSES

Not applicable.

5.3 APPENDIX 3 DEMOGRAPHICS AND BASELINE CHARACTERISTICS, PRIOR OR CONCOMITANT MEDICATIONS

Demographics, baseline characteristics, medical/surgical history

The following demographics and baseline characteristics, medical/surgical history and disease characteristics at baseline will be summarized using descriptive statistics in the enrolled population.

Demographic and baseline characteristics

- age (in years) as continuous variable and age group categorical variable
- sex (Male, Female)
- race (American Indian or Alaska Native, Asian, Black or African American, Native Hawaiian or Other Pacific Islander, White)
- ethnicity (Hispanic or Latino, not Hispanic or Latino)
- Other baseline characteristics (renal disease status, CPRA value [from local lab: OPTN-calculated, locally reported; from central lab], blood type, height, weight, body mass index [BMI], LVEF, number of prior kidney transplants, sensitizing events)

Renal disease status at study entry includes renal disease stage and duration, origin of renal insufficiency, dialysis time, and kidney waitlist information.

Other baseline safety and efficacy parameters (apart from those listed above) will be presented along with the safety and efficacy summaries.

Medical/surgical history includes any past and/or concomitant diseases or past surgeries (except previous transplantation). Medical and surgical history will be coded to a LLT, PT, HLT, HLGT, and associated primary SOC using the MedDRA version in effect at Sanofi at the time of database lock.

Other procedures

Other procedures include those not planned in the protocol that are related to or performed as a result of any AE or following a pre-existing condition. Other procedures will be coded to a LLT, PT, HLT, HLGT, and associated primary SOC using the MedDRA version in effect at Sanofi at the time of database lock.

Prior or concomitant medications, and other medications

All medications (including IR medications, prior/post-transplant immunosuppression treatments, desensitization/AMR medications) will be coded using the World Health Organization-Drug Dictionary (WHO-DD) using the version in effect at Sanofi at the time of database lock.

- Prior medications are those the participant used prior to first IMP intake. Prior medications can be discontinued before first administration or can be ongoing during treatment period.
- Concomitant medications are any interventions received by the participant concomitantly to the IMP during the on-treatment period.
- Post-treatment medications are those the participant took during the post-treatment period ([Section 4.1](#)) up to the end of the study.
- A given medication can be classified as a prior medication and/or as a concomitant medication and/or as post-treatment medication. If it cannot be determined whether a given medication was taken prior or concomitantly or post, it will be considered as prior, concomitant, and post-treatment medication.

The prior and concomitant medications and other specific medications/treatments (ie, administered for IRs, prior/post-transplant immunosuppression treatments, desensitization/AMR medications) will be summarized separately, for the enrolled and treated population, by anatomic and therapeutic level. The summaries will be sorted by decreasing frequency of anatomic category (ATC) based on incidence. In case of equal frequency, alphabetical order will be used. Participants will be counted once in each ATC category (anatomic or therapeutic) linked to the medication.

5.4 APPENDIX 4 DATA HANDLING CONVENTIONS

5.4.1 General conventions

Time since CKD stage diagnosis at study entry: (date of first IMP dose - date of diagnosis for most recent CKD stage at study entry) + 1, and convert to years

Dialysis time: (date of first IMP dose – start date of most recent start/restart chronic dialysis) + 1, and convert to years

Waitlist time: (date of first IMP dose – waitlist registration date (from transplant status at study entry)) + 1, and convert to years

Creatinine clearance (eGFR) using the equation of MDRD formula:

$$\text{GFR} = 175 \times (\text{Scr})^{-1.154} \times (\text{Age})^{-0.203} \times (0.742 \text{ if Female}) \times (1.212 \text{ if African American})$$

with serum creatinine in mg/dL and age in year.

Missing data

The analyses and summaries of continuous and categorical variables will be based on observed data only. Percentages will be calculated using as denominator the number of participants with non-missing observation in the considered population. When relevant, the number of participants with missing data is presented.

When incomplete or missing dates are found in the eCRF, attempts will be made to retrieve the complete date, especially for dates within the month prior to first IMP dose. However, if some dates remain incomplete, the following rules will be applied:

Handling of disease characteristics missing/partial dates (including medical/surgical history, renal disease status at study entry)

- If the day is missing, impute day with 1.
- If the month is missing, impute month with 1.
- If the year is missing, no imputation will be performed.

Handling of medication missing/partial dates

No imputation of medication start/end dates or times will be performed. If a medication date or time is missing or partially missing and it cannot be determined whether it was taken prior or concomitantly, it will be considered a prior, concomitant, and post-treatment medication.

For prior transplant immunosuppression treatments, following rules will be applied:

Missing/partial start date will be imputed as follows:

- If year and month exist, day is missing, impute day with 1.
- If only year exists, month and day are missing, impute both month and day with 1.
- If year, month, and day are all missing, no imputation will be applied.

Missing/partial end date will be imputed in a two-step approach as follows:

- Step 1: Use the following rule to impute end date:
 - If year and month exist, day is missing, impute day with 1.
 - If only year exists, month and day are missing, impute both month and day with 1.
 - If year, month, and day are all missing, no imputation will be applied.
- Step 2: If imputed end date is earlier than start date, set the imputed end date the same as start date.

Imputation of incomplete start date for post-transplant immunosuppression treatments and desensitization/AMR treatments/procedures

For post-transplant immunosuppression treatments and desensitization/AMR treatments/procedures, if the start date is missing, it will be imputed as follows:

- If start day and month are missing and start year is the same as treatment end year, start date will be set equal to treatment end date + 1.
- If start day and month are missing and start year is after the treatment end year, start day and month will each be set to 01.
- If start day is missing and start year and month is the same as the treatment end year and month, start day will be set equal to the treatment end day + 1.
- If start day is missing and start month is before the treatment end month and start year is the same as treatment end year, start day will be set to 01.
- If start day is missing and start month is after the treatment end month and start year is the same as treatment end year, the medication start day will be set to 01.
- If start day is missing and start month is not missing and start year is after the treatment end year, start day will be set to 01.
- If start day, start month and start year are all missing, start date will be set equal to the treatment end date + 1.

No imputation will be done for missing/partial end dates.

Handling of AEs with missing or partial date of onset

Missing or partial AE onset dates (occurrence or becoming serious) will be imputed so that if the partial AE onset date information does not indicate that the adverse event started prior to treatment or after the TEAE period, the AE will be classified as treatment-emergent. In case of AEs worsening during the study, the emergence will also be based on the cycle of worsening. No imputation of AE end dates will be performed. These data imputations are for categorization purpose only and will not be used in listings. No imputation is planned for date of AE resolution.

Handling of death with missing or partial date of death

The imputation for missing or partial death date will proceed as follows:

- If the death day is missing and the death month and year are the same as the last month and year the participant was last known to be alive, the death day will be set equal to the last day the participant was known to be alive + 1.
- If the death day is missing and the death month is after the month the participant was last known to be alive and the death year is the same as the year the participant was last known to be alive, the death day will be set to 01.
- If the death day and month are missing and the death year is the same as the year the participant was last known to be alive, the death date will be set equal to the date the participant was last known to be alive + 1.
- If the death day and month are missing and the death year is after the year the participant was last known to be alive, the death day and month will both be set to 01.

If the date the participant was last known to be alive is partial or missing, no imputation for missing or partial death date will be performed. The last date the participant was known to be alive is the latest of the following: date of last IMP dose, date of last visit performed (when the participant is known to be alive according to subject status), date of last laboratory assessment, and date of last vital signs recorded.

Handling of AEs with missing grade

If the grade is missing for one of the TE occurrences of an AE, the maximal severity on the remaining occurrences will be considered. If the severity is missing for all the occurrences, no imputation will be done and missing grades will be summarized in the “all grades” category.

Handling of missing assessment of relationship of AEs to IMP

If the assessment of the relationship to the regimen is missing, then the relationship to the IMP regimen has to be assumed and the AE considered as such in the frequency tables of possibly related adverse events, but no imputation will be done at the data level.

Handling of parameters expressed as inequality or approximation

For some parameters (such as laboratory parameters), if the value is expressed as “<xx”, “≤xx”, half of the numeric portion of the entry or limit of quantification will be used in calculations.

Analysis windows for time points

No analysis windows will be applied in the by-scheduled visit summaries.

Unscheduled visits

Unscheduled visit measurements of laboratory data, vital signs and ADA will be used for computation of baseline, the last on-treatment value, analysis according to PCSAs/NCI grade, and the shift summaries for safety.

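### SAP 5.4.1 imputes starts of post-transplant immunosuppression and desensitization from an undefined treatment end date, and ends prior-transplant immunosuppression at the earliest compatible day, so therapy timing in the medication summaries can be wrong in either direction

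*SAP*

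**What the plan says.** SAP 5.4.1 (General conventions) gives one set of start-date rules for two classes of therapy: "For post-transplant immunosuppression treatments and desensitization/AMR treatments/procedures, if the start date is missing, it will be imputed as follows".

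- Nothing known: "If start day, start month and start year are all missing, start date will be set equal to the treatment end date + 1".
- Only the year known: if "start year is the same as treatment end year, start date will be set equal to treatment end date + 1". A later year gives 1 January of that year.
- Day missing, month and year equal to those of treatment end: "start day will be set equal to the treatment end day + 1".
- Known earlier month: "If start day is missing and start month is before the treatment end month" of the same year, day 01 of the recorded month is used. A later month or year is treated the same way.
- Start year before the treatment-end year: no rule.

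The transplant date appears in none of these rules, and *treatment end date* is not defined. The SAP offers three candidates: the last dose; last dose + 14 days (the exposure definition in 4.7.1 when the last cycle is Q2W); and last dose + 30 days (the end of the on-treatment period in 4.1).

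For prior-transplant immunosuppression, a partial end date goes to day 1 of a known month. For a known year, "If only year exists, month and day are missing, impute both month and day with 1". Then "If imputed end date is earlier than start date, set the imputed end date the same as start date". A fully missing end date is left missing.

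Other medicines follow a different default. When timing cannot be determined, SAP 5.3 says "it will be considered as prior, concomitant, and post-treatment medication", and 5.4.1 repeats this without imputing any date. SAP 5.3 defines concomitant as received in the on-treatment period.

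**The concern.** Desensitization aims to lower the antibodies that the primary endpoint measures, and protocol 6.5 prohibits other desensitization and, with listed exceptions, immunosuppression until the end of site visit follow-up, early discontinuation or transplantation. For these therapies the SAP leaves its own cautious default and substitutes a single invented date, without giving a reason. A drug that is post-transplant by definition can be dated before the transplant. A desensitization course of unknown timing is fixed just after treatment end.

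The trial has no control arm and a minimum of 12 participants per cohort, so one participant is 1/12 = 8.3% of a minimum-size cohort. Whoever reads a response needs to know whether other antibody-directed therapy came before it. The medication summaries in SAP 5.3 are where that would be looked up.

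**Working it through.** The plan gives no figure to reproduce here. The check applies the stated rules to worked cases, then to a grid of dates. The calendar dates are illustrations. The grid percentages weight all true dates equally, which is an assumption, and classify by start date only.

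**1. Post-transplant immunosuppression.** Last dose 1 March 2021, transplant 15 September 2021, start recorded as 2021 only. Imputed start = treatment end + 1.

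| Treatment end read as | Date | Imputed start | Days before transplant |
|---|---|---|---|
| last dose | 1 Mar | 2 Mar | 197 |
| last dose + 14 | 15 Mar | 16 Mar | 197 − 14 = 183 |
| last dose + 30 | 31 Mar | 1 Apr | 197 − 30 = 167 |

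With the start recorded as September 2021, it becomes 1 September, 14 days early under every reading. Now let the drug start on the transplant day, with the transplant 1 to 364 days after treatment end and 365 different first-dose dates. The imputed start precedes the transplant in 96.4% of cases (day missing), 99.5% (year only) and 99.7% (all missing), whichever reading is used.

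**2. Undated desensitization.** First dose 1 March 2021, last dose on Day 71 = 10 May, on-treatment period to 10 May + 30 = 9 June. Treatment end + 1 is 11 May, 25 May or 10 June under the three readings. The first two are concomitant by SAP 5.3 and the third is post-treatment.

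For all true starts from 180 days before first dose to 26 weeks after a 12-week treatment period:

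| Recorded | True timing | Last dose | Last dose + 14 | Last dose + 30 |
|---|---|---|---|---|
| nothing | any | 100% concomitant | 100% concomitant | 100% post |
| year only | before first dose | 56.0% concomitant, 44.0% no rule | 52.2% concomitant, 47.8% no rule | 47.8% post, 52.2% no rule |
| year only | on-treatment | 93.3% concomitant, 6.7% no rule | 90.3% concomitant, 9.7% no rule | 86.3% post, 13.7% no rule |
| year only | post-treatment | 77.1% concomitant, 22.9% post | 77.1% concomitant, 22.9% post | 100% post |

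With only the day missing the damage is smaller. Truly on-treatment starts stay concomitant in 81.2%, 78.9% and 60.0% under the three readings.

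**3. Order relative to the response sample.** In the same participant, suppose a course was truly given on 5 April and recorded as 2021. Its imputed start is 11 May at the earliest. The C3D1 sample is due on 26 April (first dose + 56 days). A response first seen there would appear to precede a course that was in fact given 21 days before it. Two of the nine scheduled post-baseline central samples (C2D1 and C3D1, then follow-up Weeks 1 to 25 every four weeks) come before the last dose.

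**4. Prior-transplant immunosuppression.** First dose 10 February 2021, end recorded as January 2021.

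- Imputed end 1 January: gap 40 days.
- Latest compatible end 31 January: gap 10 days.
- Possible stop days within the 28 days of exclusion criterion E 12: 13 to 31 January, 19 of 31.

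Over true stops 1 to 365 days before first dose, and where the floor at the start date does not bind, the end moves earlier by 14.7 days on average (maximum 30) with the day missing, and by 182.5 days (maximum 365) with only the year known. Of true stops less than 28 days before first dose, 54.0% and 96.2% respectively are imputed at 28 days or more before it.

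**The case against.** The strongest reply is that little depends on these dates. Response rate (SAP 4.3) and duration of response (SAP 4.4.2.1) use no medication date. The stated use is descriptive tables, with post-transplant immunosuppression and desensitization/AMR treatment summarized separately from other medicines. Missing dates are pursued before imputation, above all those in the month before first dose. A known month before treatment end is kept. All of this stands, and it limits the point to the summaries and their interpretation.

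Four stronger readings are tempting, and the documents do not support them.

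- *A reader might infer that the rules mostly hide concurrent desensitization.* The on-treatment period runs to last dose + 30 days, so treatment end + 1 is concomitant under two of the three readings, and there the larger error is over-counting as concomitant. Only last dose + 30 gives the opposite.
- *A reader might infer bias in the response rate or duration of response.* No endpoint rule takes these dates as input.
- *A reader might infer that imputed end dates let participants pass E 12, and so enter the efficacy-evaluable population.* That population does require eligibility, but protocol section 8 has eligibility confirmed from screening evaluations, and the SAP does not say that imputed dates decide it.
- *A reader might infer that the tables will report prohibited immunosuppression that never happened.* An imputed date can fall in the prohibited window, but no planned analysis flags it against the transplant date.

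**Conclusion.** The rules are wrong as written, in a limited way. Followed exactly, they give impossible dates for post-transplant drugs, up to 197 days early in the worked case and still 167 days early under the most favourable reading of treatment end. They place undated desensitization at a date unrelated to when it was given, with a direction of error set by an undefined term. They leave start years before the treatment-end year without a rule. They also overstate the gap between prior-transplant immunosuppression and first dose.

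The size in this trial cannot be stated. The documents give no frequency of partial dates, retrieval comes first, and the percentages rest on equally weighted true dates. What is at risk is the accuracy of the medication summaries, and the reading of individual responses against other therapy in two small single-arm cohorts. The correction is worth making because it costs little and holds under every reading of treatment end.

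**What to change.** In SAP 5.4.1:

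- (a) Define *treatment end date*. For post-transplant immunosuppression, make the transplant date the lower bound: the imputed start is the later of the transplant date and the first day compatible with the recorded part.
- (b) For desensitization/AMR treatment, drop the rule that sets the start to the day after treatment end. Apply the existing SAP 5.3 default and count the treatment in every period that the known part of its date allows, including start years before the treatment-end year. A fully undated course then appears in all three periods under any definition of treatment end.
- (c) Impute partial end dates of prior-transplant immunosuppression to the latest compatible day. Do not cap them at the day before first dose unless the record shows that the drug had stopped by then. With first dose on 10 February 2021 and an end recorded as 2021, only 40 of 365 compatible days precede first dose, so a cap would assert a stop that the record does not show.

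The cost is SAP wording and minor programming. The tables may show slightly more prior or concomitant therapy.
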